9.2.1.2 Index Date

Depending on the date of first evidence of AF over the study period, AF patients will be included at the following dates:

- On 1st January 2016 for **prevalent AF patients** (i.e., patients diagnosed AF during the historical period);
- On the first date of evidence of AF (first date of diagnosis of AF identified either by a LTD or the start date of a hospitalization, or the first date of OAC dispensation) for **incident AF patients**.

A patient will be considered exposed to OAC at the time of his/her inclusion if at least one dispensation of OAC is issued within 30 days after inclusion (including date of inclusion). In such a case, the index date will be the date of the first dispensation of OAC (cf. Appendix 1).

Otherwise, if no dispensation of OAC will be identified within 30 days from inclusion, the index date will be the date of inclusion.

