9.2.1.4 Follow-up and Censoring

[figure not shown]
The Follow-up period starts at index date and ends on the date of occurrence of one of the following events:

- Death;
- End date of the study fixed to December 31st, 2019 or to December 31st, 2020 for sensitivity analyses;

- Date of the last reimbursement of care recorded in the SNDS (patients with no consumption or reimbursement of care in the 12 months following the date of last consumption).

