Number of occurrences	
Continuous variable
 
Equals to the number of occurrences where the two criteria are met:
 
 - The variable HCRU equals to the specified HCRU - The value of the variable Date of care falls in the specified time period
Rate of occurrences per patient-month	
Continuous variable (occurrence in month)
 
Equals to the value of the variable Number of occurrences divided by the duration of follow-up in month of the specified time period

Total cost HCRU	
Continuous variable (euros)
 
Equals to the sum of the values of the variable Cost where the two criteria are met:
 
 - The variable HCRU equals to the specified HCRU - The value of the variable Date of care falls in the specified time period

9.4.3.6 *Description of the therapeutic management before/after the first stroke occurring after initiation of OAC therapy*

Table XIX. Derived variables for the description of therapeutic management at 6 and 12 months before / after the first stroke occurring after initiation of AOC therapy

Variable	Definition
HCRU after first stroke	
Categorical variable (Ambulatory care/hospital care/rehabilitation care facilities/medications related to AF)
 
Equal to:
 
 - “Ambulatory care” if the reimbursement corresponds to any outpatient physician’s visits (private practice, home or outpatient) or outpatient paramedic visits or dispensing of observable drugs (AF drugs and other) - “Hospital care” if the reimbursement corresponds to any Hospital admission or Hospital at home or Palliative care or Emergency visit - “Rehabilitation care facilities” if the reimbursement corresponds to any SSR stays - “Medication related to AF” if the reimbursement corresponds to any anticoagulants, antiplatelets, antihypertensive drugs glucose-lowering drugs, lipid-lowering drugs, antiarrhythmics or beta-blockers
Date of care	
Date variable
 
Equals to the value of date of care indicated in the data extraction and associated with the reimbursement

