- Counts and percentages of patients with at least 1 reimbursement of specific OAC or no reimbursement for patients unexposed to OAC.
- Mean, SD, median, Q1, Q3, min and max of the rate of reimbursements per patient per month of follow-up in patients with at least 1 reimbursement of specific OAC or no reimbursement for patients unexposed to OAC.

All costs will be provided in Euros, annualized based on 2019 prices and presented per patients per month (PPPM) to consider differences in follow-up duration. Cost analysis will be performed from the health insurance perspective (reimbursed costs).

For the comparison of average of the overall PPPM costs (e.g. during all the follow-up) between AF incident patients exposed to apixaban, rivaroxaban, dabigatran vs NVAF patients exposed to VKA, significant differences between groups will be detected with an ANOVA for global equality of means. In case of the global test is significant, Tukey post-hoc test will be calculated to evaluate pair comparison. Normality will be tested before processing the analyses by the evaluation of the residuals (QQ plot and Shapiro-Wilk test) and homogeneity of variance with the Levene test and the plot of residuals versus fits. If normality not verified, Kruskal-Wallis test will be used. If homogeneity not verified, the Welch ANOVA will be used and Games-Howell for post-hoc test. The tests will be two-sided with a significance level of 5%.

9.7.4.6 Description of the therapeutic management before/after the first stroke occurring after initiation of OAC therapy

HCRU overall and for each resource (ambulatory care, hospital care, rehabilitation care facilities and medications) will be described at 6 and 12 months before and after the first stroke occurring after initiation of OAC therapy for patients exposed to apixaban, rivaroxaban, dabigatran and VKA in term of :

- Counts and percentages of patients with at least 1 reimbursement HCRU.

- Mean, SD, median, Q1, Q3, min and max of the rate of reimbursements per patient per month of follow-up in patients with at least 1 reimbursement of HCRU.

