Q1 - Q3	xx.x - xx.x	xx.x - xx.x	xx.x - xx.x	xx.x - xx.x	xx.x - xx.x
Min - Max	xx.x - xx.x	xx.x - xx.x	xx.x - xx.x	xx.x - xx.x	xx.x - xx.x
IC 95%	(xx.x - xx.x)	(xx.x - xx.x)	(xx.x - xx.x)	(xx.x - xx.x)	(xx.x - xx.x)

All cost are calculated per patient per month (PPPM)

< Time period >:

6. All: 2016-2019

7. 2016

8. 2017

9. 2017

10. 2018

11. 2019

Table A16. Overall comparison of HCRU and associated cost (during all the follow-up)

	Cost				Anova/Welch test/ Kruskall-Wallis*		Tukey test / Games- Howell test*	
	N (%)	Mean (std)	Median (Q1-Q3)	Min-Max	F	p-value	p-value	Sig**
All cost (2016-2019)								
Total								
Apixaban	xx (x.x)	xx.x (xx.x)	xx.x – xx.x	xx.x – xx.x	x.xx	x.xx	x.xx	ns/*
Dabigatran	xx (x.x)	xx.x (xx.x)	xx.x – xx.x	xx.x – xx.x			x.xx	ns/*
Rivaroxaban	xx (x.x)	xx.x (xx.x)	xx.x – xx.x	xx.x – xx.x			x.xx	ns/*
Unexposed	xx (x.x)	xx.x (xx.x)	xx.x – xx.x	xx.x – xx.x			x.xx	ns/*
VKA (ref)	xx (x.x)	xx.x (xx.x)	xx.x – xx.x	xx.x – xx.x				

All cost is calculated per patient per month (PPPM)

*Test considered depend on verification of the hypothesis

*Post hoc comparisons type of exposure and unexposed vs. VKA (ref) : ***p<0.001, **p<0.01, *p<0.05

3.7. Description of the therapeutic management before/after the first stroke occurring after initiation of OAC therapy

Table A17. Number of occurrences of HCRU 6 and 12 months before and after the first stroke for patients exposed to OAC

	Apixaban (N=XXX)	Dabigatran (N=XXX)	Rivaroxaban (N=XXX)	VKA (N=XXX)	All exposed (N=XXX)
HCRU					
From 12 to 6 months before 1 st stroke date					
n* (%)	xx (x.x)	xx (x.x)	xx (x.x)	xx (x.x)	xx (x.x)
Mean (std)	xx.x (xx.x)	xx.x (xx.x)	xx.x (xx.x)	xx.x (xx.x)	xx.x (xx.x)
Median	xx.x	xx.x	xx.x	xx.x	xx.x
Q1 - Q3	xx.x - xx.x	xx.x - xx.x	xx.x - xx.x	xx.x - xx.x	xx.x - xx.x
Min - Max	xx.x - xx.x	xx.x - xx.x	xx.x - xx.x	xx.x - xx.x	xx.x - xx.x
From 6 months to the 1 st stroke date					
n* (%)	xx (x.x)	xx (x.x)	xx (x.x)	xx (x.x)	xx (x.x)
Mean (std)	xx.x (xx.x)	xx.x (xx.x)	xx.x (xx.x)	xx.x (xx.x)	xx.x (xx.x)
Median	xx.x	xx.x	xx.x	xx.x	xx.x
Q1 - Q3	xx.x - xx.x	xx.x - xx.x	xx.x - xx.x	xx.x - xx.x	xx.x - xx.x
Min - Max	xx.x - xx.x	xx.x - xx.x	xx.x - xx.x	xx.x - xx.x	xx.x - xx.x
From 1 st the stroke date to 6 months after					
n* (%)	xx (x.x)	xx (x.x)	xx (x.x)	xx (x.x)	xx (x.x)
Mean (std)	xx.x (xx.x)	xx.x (xx.x)	xx.x (xx.x)	xx.x (xx.x)	xx.x (xx.x)
Median	xx.x	xx.x	xx.x	xx.x	xx.x
Q1 - Q3	xx.x - xx.x	xx.x - xx.x	xx.x - xx.x	xx.x - xx.x	xx.x - xx.x

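### Resource use per patient-month, and by implication cost, is an equal-weight mean of individual ratios, so very short follow-up can drive the tabulated means, SDs and cost confidence intervals

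*SAP*

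**What the plan says.** For resource use, SAP section 9.4.3.5 (Table XVIII) derives one rate per patient: "Equals to the value of the variable Number of occurrences divided by the duration of follow-up in month of the specified time period". Section 9.7.4.5 summarises these rates without weights: "Mean, SD, median, Q1, Q3, min and max of the rate of reimbursements per patient per month of follow-up".

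For cost, Table XVIII derives only a total in euros: "Equals to the sum of the values of the variable Cost where the two criteria are met". Section 9.7.4.5 says that costs will be "presented per patients per month (PPPM) to consider differences in follow-up duration", but no formula for that quantity is written. The shells ask for its mean, standard deviation, median, quartiles and range, and Table A15 also for a 95% CI. Their footnotes read "All cost are calculated per patient per month (PPPM" (Table A15) and "All cost is calculated per patient per month (PPPM" (Table A16). A standard deviation, median and range across patients need one ratio per patient.

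On follow-up, section 9.2.1.4 says: "The Follow-up period starts at index date and ends on the date of occurrence of one of the following events". Death is one of those events, and no minimum length is set. Under section 9.2.1.2 an incident patient may enter on "the start date of a hospitalization, or the first date of OAC dispensation". If an anticoagulant is dispensed within 30 days, the index date moves to that dispensation; otherwise it stays at inclusion. Objective 6 uses all newly diagnosed patients (section 9.2.3.3.2), and Table A15 is repeated by calendar year.

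**The concern.** Dividing by follow-up is meant to make patients with unequal follow-up comparable. Averaging the individual quotients with equal weight does the reverse for the mean: the shorter a patient's follow-up, the larger that patient's possible influence. A hospital stay spread over a few days becomes a very large monthly cost and counts as much as a patient followed for years. The result is not the insurer's cost per patient-month, although the insurer's is the stated perspective.

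The effect is not neutral between groups. A patient admitted with AF who dies in that stay with no dispensation is unexposed, with the stay in the numerator and a few days in the denominator. A patient classed as exposed must have survived to the first dispensation, where follow-up starts. The unexposed group is one of the objective 6 comparison groups and has a row in Table A16, so part of the tabulated difference could come from the averaging method.

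**Working it through.** The documents give no PPPM mean, cost, SD or early-death share, so there is no figure to reproduce. The check compares two estimators on assumed inputs.

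**Inputs (all assumed).** Every patient has an index stay costing K = 5,000 EUR. A share q dies at time t. The others are followed for T months and cost a further c per month.
- Set A: c = 400 EUR, T = 24 months, death on day 7, so t = 7/30.4375 = 0.230 month.
- Set B: c = 300 EUR, T = 22 months, t = 0.25 month.

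**Individual ratios.**
- Early death, K/t: 21,741 (A) and 20,000 (B) EUR per month.
- Others, (K + cT)/T: 14,600/24 = 608.3 (A) and 11,600/22 = 527.3 (B) EUR per month.

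**Estimators.**
- Mean of ratios = q(K/t) + (1 − q)(K + cT)/T.
- Pooled = [qK + (1 − q)(K + cT)] / [qt + (1 − q)T].

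| Set | q | Mean of ratios (EUR/month) | Pooled (EUR/month) | Multiple |
|---|---|---|---|---|
| A | 1% | 217.4 + 602.3 = 820 | 14,504/23.76 = 610 | 1.34 |
| A | 5% | 1,087.1 + 577.9 = 1,665 | 14,120/22.81 = 619 | 2.69 |
| B | 1% | 200 + 522 = 722 | 11,534/21.78 = 530 | 1.36 |
| B | 5% | 1,000 + 500.9 = 1,501 | 11,270/20.91 = 539 | 2.79 |

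**Spread.** In set A at q = 1%, early deaths alone give an SD of √(0.01 × 0.99) × (21,741 − 608) ≈ 2,103 EUR around a mean of 820.

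**Sensitivity.** In set A, early deaths supply half of the mean when q = 608.3/(21,741 + 608.3) = 2.7%. With death on day 1 that share is 0.4%; on day 30 it is 10.7%. At q = 1% with death on day 30 the multiple is only 1.07, and early deaths supply 8% of the mean. Over all settings tried (stay of 2,000 or 5,000 EUR, 400 or 800 EUR per month, 12 or 24 months, q from 0.5% to 10%, death on days 1 to 30), their contribution ran from about 2% to 97%.

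**Simulation.** 400,000 patients per setting were drawn with assumed inputs: skewed costs, early deaths on days 1 to 14, other follow-up uniform from 1 to 48 months. Results in EUR per month:

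| Early-death share | Mean of ratios | Pooled | Median |
|---|---|---|---|
| 0% | 814 | 605 | 570 |
| 1% | 1,183 | 607 | 576 |
| 5% | 2,546 | 615 | 603 |
| 10% | 4,316 | 626 | 640 |

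With no early deaths the mean of ratios already exceeds the pooled value, because other follow-up is sometimes short.

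**Calendar-year slices.** One admission with three days left in the year counts as 30.4375/3 = 10.1 admissions per month. Over 24 months the same admission counts as 1/24 = 0.04. No death is needed.

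**The case against.** Four points on the other side carry weight.

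First, medians and quartiles are already planned, and section 9.7.4.5 moves to Kruskal-Wallis if normality fails. The skew described here would probably trigger that route, and in the simulation the median moves only from 570 to 640 EUR as the early-death share goes from 0 to 10%. This stands, and it limits the effect on the test. It does not protect the tabulated means, SDs and cost intervals. The ANOVA and Welch routes also compare means, and the SAP does not say which fallback prevails when both normality and equal variance fail.

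Second, the per-patient cost ratio is inferred from the shells, not stated. That is correct, and the missing formula is itself a gap to close.

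Third, the mean individual ratio and the pooled rate are different quantities. The pooled rate gives little weight to patients who die early, and follow-up ended by death is informative. This is a fair reason to keep the unweighted mean as description. Against it, the SAP already pools for its primary objective (section 9.7.3.1: events over summed follow-up), and pooling serves the stated purpose of PPPM.

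Fourth, a reader might go further and infer that early deaths do dominate the means, or that the VKA group will also look several times more expensive. The documents support neither. They give no early-death share and no mortality by drug, and the index-stay mechanism points to the unexposed group, because VKA patients must survive to a dispensation. Charging the stay only to patients who die would raise the multiples to 1.6 (497 against 302 EUR at 1%) and 4.1 (1,285 against 312 EUR at 5%) on set B's other inputs. Survivors can also enter through a hospital stay, so that contrast is too favourable to the criticism.

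**Conclusion.** The concern holds in a conditional form. The SAP averages individual resource-use ratios with equal weight and implies the same for cost, with no safeguard for very short follow-up. The resulting means, SDs and cost intervals can be dominated by patients observed for days, and early deaths in the index stay fall on the unexposed side. Under the assumptions shown, the mean of ratios is about 1.3 to 1.4 times the pooled value at a 1% early-death share and 2.7 to 2.8 times at 5%. Later deaths or cheaper stays make it smaller; deaths in the first days make it larger. The true size cannot be known until the share and timing of early deaths are tabulated. The effect on medians and on a rank test is much smaller. This concerns one secondary objective and should be settled before the cost tables are produced.

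**What to change.** Amend SAP sections 9.4.3.5 and 9.7.4.5 and the shells of Tables A15 and A16:

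1. Write the formula for cost PPPM, which is currently missing.
2. Make the headline PPPM for each group and period the total cost (or total occurrences) divided by total patient-months, with a patient-level bootstrap 95% CI.
3. In Table A16, compare each group with VKA on this estimate, using the same bootstrap, alongside the planned test.
4. Keep the per-patient median and quartiles, and the unweighted mean if wanted, as description only.
5. State a rule for zero or near-zero follow-up, and report by group how many patients it affects. Reconcile the recorded precision of the date of death first: Protocol Appendix 1 lists month and year, while SAP section 9.3.1.2 lists a date of death without that limit. If only the month is held, follow-up of early deaths cannot be counted in days.

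The cost is SAP wording and slightly more programming, with no new data. The headline means will probably be lower than unweighted ones. Pooling stops short denominators from being magnified, but it does not remove the underlying asymmetry that exposed patients must survive to a dispensation. The report should say so.

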9.4.4 Exploratory Outcomes

Table XX. Variables to identify subgroups among AF patients with similar profile

Variable	Definition
Sociodemographic characteristics	Age/Sex/CMU-c/ACS/Region of residence/Frail patient/Modified CHAD ₂ DS ₂ VASC score/HAS-BLED score See Table V/XII
Medical history and comorbidities	Ischemic or hemorrhagic stroke/CAD/Dementia/ Congestive Heart failure/ Peripheral arterial disease/ Other vascular diseases/ Sleep disorders/ Active cancer/Charlson score/ Malnutrition/ Morbid Obesity/ Anemia/ COPD/ Diabetes history/ Risk of falls/ Poly-medicated/ At least one visit to a nursing home/ History of major bleeding/ One or more comorbidities See Table V/XII
Concomitant treatments	Binary variable (Yes / No) Equals to “Yes” if the patient has reimbursements for at least one dispensation at pharmacy of Beta-blockers/ Antihypertensives/ Antiplatelet drugs/ Other anticoagulants/ Non-steroidal anti-inflammatory drugs (NSAIDs)/ Oral corticoids/ Proton pump inhibitors/ Selective serotonin reuptake inhibitor antidepressants (SSRIs)/ Systemic azole antifungals/ Medical procedure of cardioversion/ CYP P450 inhibitors/ Protease inhibitors/ Antiarrhythmics/ Glucose-lowering drugs/ Lipid-lowering drugs/ Digitalis glycosides/ Nitrate derivatives during the follow-up period Equals to “No” in the other case
Event of interest	Stroke (ischemic or hemorrhagic)/ Major bleeding/ Death See Table V/VIII
Event of interest: Number of occurrences	Number of occurrences See Table V/XI
OAC at start follow-up date	Categorical variable (VKA / Apixaban / Dabigatran / Rivaroxaban / Unexposed)

	See Table V XII
OAC treatment pattern	New user of OAC/VKA/Apixaban/Rivaroxaban/Dabigatran/ Number of sequence treatment/ Duration of each OAC/ Switch of OAC treatment/ Temporary or permanent discontinuation/ Concomitant treatments/ Type of delivery/ Prescriber's specialty
	See Table V XVII
HCRU	Number of occurrences/ Total cost HCRU

See [Table V XVIII](#)

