9.7.5 Planned Analysis for the Exploratory Objective

9.7.5.1 Identification of subgroups among patients with similar profile with clustering models

The identification of subgroups among patients with similar profile will be descriptive and exploratory in nature with the variables listed in the table XX. The analysis will be run following the clustering models like K-Means, Random-Forest or Ascending hierarchical clustering. Data visualization will be also presented.

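### The clustering inputs in SAP Table XX include outcome events and totals accumulated over unequal follow-up, so the exploratory subgroups would partly reflect entry date rather than patient profile.

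*SAP*

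**What the plan says.** SAP 9.7.5.1 ties the clustering to one variable list. It says that the identification of subgroups with "similar profile will be descriptive and exploratory in nature with the variables listed in the table XX". It names K-means, random forest and hierarchical clustering, but gives no scaling, distance, number of clusters or stability check.

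Table XX in SAP 9.4.4 is that list. Besides sociodemographics, scores, medical history and the anticoagulant at the start of follow-up, it contains:

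- the events "Stroke (ischemic or hemorrhagic)/ Major bleeding/ Death", and in a further row "Event of interest: Number of occurrences";
- 17 concomitant treatments coded ever/never, in a list ending "Digitalis glycosides/ Nitrate derivatives during the follow-up period";
- treatment-pattern items including "Number of sequence treatment/ Duration of each OAC/ Switch of OAC treatment/ Temporary or permanent discontinuation";
- for resource use, "Number of occurrences/ Total cost HCRU".

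Table XVIII (SAP 9.4.3.5) already derives a time-adjusted resource rate: "Equals to the value of the variable Number of occurrences divided by the duration of follow-up in month of the specified time period". Table XX does not use it. It takes the raw count and the total cost, the latter defined as "Equals to the sum of the values of the variable Cost where the two criteria are met" for a time period that Table XX never sets.

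Entry runs from 1 January 2016 to 31 December 2019 (SAP 9.2.1.1). Follow-up ends at death, at the last reimbursement, or on 31 December 2019 in the main analysis (SAP 9.2.1.4).

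**The concern.** Objective 8 is to find AF patients with a similar profile. A patient who entered in early 2016 has up to four years in which to accumulate drugs, contacts, costs, treatment sequences and events. A patient who entered in late 2019 has almost none. If those totals go in without adjustment, many of the inputs carry a shared signal, length of follow-up, and a distance-based method will tend to find it. Length of follow-up depends mainly on calendar date of entry and on early death.

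There is a second, separate problem. If stroke, bleeding and death help to form the clusters, a later statement that one cluster has more strokes than another is circular.

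At stake is how the subgroups are interpreted. They could look reproducible and be read as clinical phenotypes while partly reflecting when patients entered the cohort.

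**Working it through.** The documents give no figure for this analysis, so there is nothing to reproduce. The check has four steps.

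**1. Count the inputs in Table XX.** Baseline: 8 sociodemographic items and scores + 19 history items + 1 anticoagulant at start = 28. Follow-up: 17 concomitant treatments + 3 events + 3 event counts + 12 treatment-pattern items + 28 resource variables = 63. The 28 assumes a count and a cost for each of the 14 categories in Table XVIII; Table XX does not say how resource use is split.

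**2. Two patients with identical care.** Both survive to 31 December 2019 and have one contact a month. Entry on 1 January 2016 gives 48 contacts; entry on 1 January 2019 gives 12, a ratio of 4. With an assumed bleeding rate of 0.03 per year, the chance of a recorded bleed is 1 − exp(−0.03 × 4) = 11.3% against 1 − exp(−0.03 × 1) = 3.0%. The per-month rates are the same.

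**3. Simulation with no profile structure.** All patients have the same event hazards, and entry is uniform over 4 years with a common end. Inputs mirror Table XX. Assumptions not in the documents: death 0.05, 0.10 or 0.20 per year; stroke 0.02 and bleeding 0.03 per year; between-patient variance in resource use 0.2, 0.5 or 2. The measure is eta-squared, the share of variance in follow-up length explained by cluster.

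| Inputs | Clusters (k) | Share of follow-up variance |
|---|---|---|
| Table XX, standardised k-means | 2, 3, 5 | 57-81% |
| Table XX, standardised Ward, variance 0.2 or 0.5 | 2, 3, 5 | 53-59% |
| Table XX, standardised Ward, variance 2 | 2, 3, 5 | 25-43% |
| Table XX, unscaled k-means | 2 | 2-3% |
| Table XX, unscaled k-means | 5 | 31-46% |
| Only the events removed, k-means | 2 | 64-66% |
| Costs per patient-month, rest raw, k-means | 2 | 55-65% |
| All resource use removed, k-means | 2 | 51% |
| Baseline + events + resource rates, k-means | 2, 3, 5 | 0-3% |
| Baseline only, or baseline + resource rates | 2-4 | 0-1% |

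A second no-structure simulation gave 28-65% with Table XX inputs. Random forest clustering was not among the runs reported here.

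Split-half agreement for Table XX inputs (adjusted Rand index) was 0.90-0.92 at k=2 and 0.83-0.89 at k=3, so the artefact would look stable. In one k=2 run with death at 0.10 per year, the two clusters had mean follow-up of 2.48 and 0.59 years, deaths in 13% and 26%, strokes in 5% and 1%, and bleeds in 8% and 2%. The shorter-follow-up cluster had twice the deaths (26/13) but one fifth of the strokes (1/5) and one quarter of the bleeds (2/8).

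Outcomes separate unevenly. Clusters explained 2-5% of the variance in death with k-means and at most 2% with Ward. For stroke and bleeding, clusters made up of patients with the event usually formed at k=4-5. Keeping the events while removing the other accumulated inputs cured the sorting by follow-up (0-3%), but clusters then explained up to 100% of the stroke variance at k=5. Both groups of inputs therefore need attention.

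**4. Simulation with a strong two-class baseline profile.** Agreement with the true classes (adjusted Rand index):

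| Inputs | k=2 | k=4 |
|---|---|---|
| Table XX | 0.00 | 0.26 |
| Baseline only | 0.74 | 0.38 |
| Baseline + resource rates | 0.82 | 0.65 |

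With a moderate profile, the k=2 values were 0.00 for Table XX and 0.23-0.27 for the two repaired sets.

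**The case against.** The strongest defence is that the plan never says the profile is a baseline profile. SAP Table XXI classes the analysis as longitudinal over 2016-2019 and lists TAK among the methods, so a typology of care pathways is a plausible aim. No comparison of events between clusters is planned. The analysis is labelled exploratory, Appendix 3 has no shell table for it, and no decision depends on it. Table XVIII refers to a specified time period, so a fixed window for resource use could still be chosen. Scaling is unspecified, and the result depends on it.

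Much of this stands. It limits the severity and means that baseline-only inputs are one sound repair among several. The circularity is a warning about a use that readers may make, not an error in a planned test. It does not remove the problem, because a longitudinal typology also has to handle time at risk: otherwise the two patients in step 2 look different although their care is the same. Nor would a fixed window for resource use alone be enough, since dropping resource use altogether still left 51% at k=2. Unscaled k-means avoids most of the sorting by follow-up at k=2, but only because cost in euros dominates.

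That k-means returns groups from structureless data is true of any inputs and is not the point. The point is that these groups are stable and track follow-up.

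**Conclusion.** The concern holds for exploratory objective 8 only; primary and secondary objectives are unaffected. With standardised Table XX inputs and no true profile structure, clusters explain roughly 30-80% of the variance in follow-up length, against 0-1% for index-date variables with or without resource rates. This rests on the simulation assumptions above and on standardisation, which the SAP does not specify.

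A reader might infer more, and the documents do not support it:

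- **That follow-up accounts for over 80% as a rule.** One set-up with 36 mutually independent baseline and 30 follow-up inputs gave 82-88%, but that depends on its assumptions. Other settings gave much less.
- **That the clusters sort patients by death.** The separation is weak, even where the proportion dying doubles between clusters. A small p-value at n = 10,000 or more says little about separation.
- **That every follow-up input is length of follow-up in disguise.** Prescriber specialty and type of delivery are not, and switching also reflects treatment behaviour.
- **That the analysis cannot answer objective 8.** The objective does not define profile, and Table XX inputs recovered part of a strong structure at k=4. The supportable statement is that the subgroups would partly reflect entry date.

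**What to change.** Amend Table XX and SAP 9.7.5.1:

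1. Restrict the clustering inputs to index-date variables: sociodemographics, scores, medical history, concomitant treatments in the 4-month pre-index window of Table XIV, and anticoagulant at index.
2. If treatment-pattern or resource profiles are wanted, say so, and enter them only as per-patient-month rates or over a fixed window in patients with complete follow-up of that window.
3. Remove stroke, major bleeding, death and their counts from the inputs. Describe them by cluster afterwards as rates per person-year.
4. State the scaling, how the number of clusters is chosen, and a stability check.

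Before Table XIV is used for this, its glucose-lowering and lipid-lowering rows need correcting: their ATC codes are exchanged relative to Protocol Appendix 5.

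The cost is SAP wording; the main variables are already derived and no new data are needed. The downside is a narrower set of inputs or, with a fixed window, the loss of patients with short follow-up.
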